#### **6.2.9** Unscheduled Visits

Only scheduled post-baseline values will be tabulated. Post-baseline repeat / unscheduled assessments will be disregarded, although these post-baseline assessments will be listed in the relevant appendices to the CSR.

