8.9 Subject Stopping Rules

If, in the opinion of the investigator, the participation in the study is or is becoming detrimental to the well-being of a particular subject, this issue should be discussed with the Medical Monitor for this study and dosing may be discontinued.

Subjects that experience a Grade 4 or greater toxicity according to the Common Terminology Criteria for Adverse Events (CTCAE) version 4 (https://evs.nci.nih.gov/ftp1/CTCAE/CTCAE 4.03 2010-06-14 QuickReference 5x7.pdf)

that is deemed to be possible, probably or definitely related to study drug will be discontinued from the study. Prior to discontinuation from the study, the grading of the event and causal relationship should be discussed with the Medical Monitor for the study.

Subjects will be discontinued from dosing if AST or ALT levels are >5 times the upper limit of normal, or if AST or ALT levels are >3 times the upper limit of normal along with a total bilirubin elevation of >2 times the upper limit of normal.

Subjects will be discontinued from dosing if Grade 3 diarrhea is observed.

Subjects will be discontinued from dosing if Grade 3 neutropenia is observed.

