#### 6.2.1 Baseline

Baseline is defined as the last non-missing value (either scheduled, unscheduled or repeat) before the subject receives the first dose of study drug.

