# 6.15.4 Physical Examination

Shift tables for each body system from baseline to worst post-baseline record will be presented (Normal, Abnormal NCS and Abnormal CS). NCS = Abnormal Not Clinically Significant, CS = Clinically Significant.

All physical examination data will be listed.

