# 6.15.5 Electrocardiogram Data

Descriptive statistics for observed values and changes from baseline in the following ECG variables will be tabulated at each follow-up visit:

- Heart rate (bpm)
- PR interval (ms)

QMD Ref: Worldwide-TMP-ST-005-7.0 Effective: 12Aug2019	Governing QMD: Worldwide-SOP-ST-001	
Confidentiality Statement		
This document is the property of Worldwide Clinical Trials Inc. and may not be duplicated, copied, altered or removed from company without		
prior approval from Worldwide Quality Assurance or in compliance with Worldwide Standard Operating Procedures.		

Worldwide Clinical Trials Controlled Quality Management Document		
WORLDWIDE CLINICAL TRIALS	Sponsor:	Veru Inc.
	Protocol Number:	V0211901
STATISTICAL ANALYSIS PLAN. PHASE 2-3-4		

- RR interval (ms)
- QRS duration (ms)
- QT interval (ms)
- QTc interval (ms)
- QTc interval (ms) [Bazett's formula QTcB]
- QTc interval (ms) [Fridericia's formula QTcF]

Shift tables in relation to the overall interpretation (Normal, Abnormal NCS and Abnormal CS) from baseline to worst post-baseline record will be presented.

All ECG data will be listed.

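### The SAP's rule to tabulate only scheduled post-baseline values conflicts with its physical-examination and ECG shift tables, which promise the worst post-baseline record

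*SAP*

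**What the plan says.** SAP 6.2.9 sets a general rule for tables: "Only scheduled post-baseline values will be tabulated". It continues: "Post-baseline repeat / unscheduled assessments will be disregarded". The same sentence keeps these assessments in the listings of the study report.

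Two safety sections then use different language. For the physical examination, SAP 6.15.4 says: "Shift tables for each body system from baseline to worst post-baseline record will be presented". For the ECG, SAP 6.15.5 says: "Shift tables in relation to the overall interpretation (Normal, Abnormal NCS and Abnormal CS) from baseline to worst post-baseline record will be presented". Neither says whether repeat or unscheduled records count towards the worst one.

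The laboratory section (SAP 6.15.2) and the chest imaging section (SAP 6.15.6) do not use the word worst. Their shift tables run from baseline to each timepoint.

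**The concern.** An unscheduled ECG or examination is often done because something has changed in the subject. A shift table to the worst record exists to catch such a change whenever it occurs. If 6.2.9 governs, the two tables carry a label they do not meet, because a worse record from outside the visit schedule is left out.

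The schedule makes this matter more here than it would in a trial with frequent visits. After baseline there are only three planned ECGs and three planned examinations, the first on Day 15. Dosing lasts at most 21 days and ends earlier if the subject leaves hospital. What is at stake is whether the by-arm summary of ECG and examination abnormalities is complete. Efficacy results are not affected.

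**Working it through.** The plan gives no figure on this point, so there is nothing to reproduce. The check is a comparison of sections, followed by one illustrative count.

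**1. The schedule.** Protocol 8.5 to 8.7 and Appendix B place post-baseline 12-lead ECGs and physical examinations on Day 15, Day 22 (±3 days) and Day 29 (±3 days). Protocol 8.6 adds the Day 22 set at early termination or discontinuation from the study. I treat that visit as scheduled because the protocol specifies it; the SAP does not say.

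**2. The rule applied to the tables.**

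| SAP section | Summary | Records used if 6.2.9 is followed literally |
|---|---|---|
| 6.15.4 | Examination, shift to worst | Days 15, 22, 29 or early termination |
| 6.15.5 | ECG, shift to worst | Days 15, 22, 29 or early termination |
| 6.15.2 | Laboratory, shift to each timepoint | Scheduled timepoints; no conflict |
| 6.15.6 | Chest imaging, shift to each timepoint | Scheduled timepoints; no conflict |

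The contradiction is therefore confined to the first two rows.

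**3. Does the SAP signal exceptions elsewhere?** Yes. SAP 6.12.2.3 says that the fever and oxygen saturation responder status uses all vital sign and log data. SAP 6.12.3.1 says that the WHO-scale area under the curve uses every available measurement to Day 15. For baseline, SAP 6.2.1 is equally explicit: "Baseline is defined as the last non-missing value (either scheduled, unscheduled or repeat) before the subject receives the first dose of study drug". Sections 6.15.4 and 6.15.5 contain no comparable statement, so a programmer has no stated ground for departing from 6.2.9.

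**4. Subjects discharged early.** Dosing stops at discharge (Protocol Appendix B, footnote b). For a subject discharged before Day 15, every scheduled post-baseline ECG and examination falls after dosing has ended, unless early termination from the study brings one forward. An in-hospital ECG in that subject would be unscheduled and outside the table.

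**5. How sparse the schedule is (illustration only).** Three assumptions, none from the documents: onset is equally likely on each of Days 1 to 21, visits fall exactly on Days 15, 22 and 29, and the subject is still being assessed. An abnormality starting on day *o* and lasting *d* days overlaps a visit on day *v* if *o* ≤ *v* ≤ *o* + *d* − 1. Counting onset days that overlap at least one visit:

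- *d* = 1: onset on Day 15, so 1/21 = 4.8%
- *d* = 2: Days 14, 15, 21, so 3/21 = 14.3%
- *d* = 3: Days 13–15, 20, 21, so 5/21 = 23.8%
- *d* = 7: Days 9–21, so 13/21 = 61.9%

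Under these assumptions, a short-lived finding would usually miss the scheduled records. The complement is not the share lost through 6.2.9. For that rule to remove a finding, an unscheduled assessment must also have recorded it.

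**6. Weight of one subject.** With 20 subjects planned per arm (SAP 5), one subject is 1/20 = 5 percentage points of that arm.

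**The case against.** The strongest reply is that the specific wording overrides the general rule. The SAP uses each timepoint for laboratory and imaging tables and worst record for examination and ECG, which could mean that all records were intended for the latter. That reading is possible, but the SAP does not state it, and it does state the point in the two efficacy sections where all data are meant. The text must settle the matter either way.

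A second reply is that other outputs cover the gap, and much of this stands. Treatment-emergent and serious adverse events are tabulated by arm whichever visit revealed them (SAP 6.15.1). All examination and ECG data are listed, with listings sorted by treatment group first (SAP 6.3), so in about 40 subjects a reader could count by hand. The safety board reviews unblinded data every two weeks (Protocol 9.7.1). A reader might infer that acute safety abnormalities vanish from the arm comparison; these routes show that the documents do not support so strong a statement. What remains uncovered by a table is an abnormal ECG or examination not reported as an adverse event, or arising outside the treatment-emergent window, which closes at last dose plus 7 days.

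A reader might also carry the criticism over to laboratory results, on the ground that Protocol 8.9 ties dosing discontinuation to liver and neutrophil values. The laboratory shift tables are by timepoint and contradict nothing, and SAP 6.15.2 places a listing of clinically significant laboratory results from the whole study in the tables section. A worst-value laboratory summary would be an improvement, not a correction.

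Finally, allowing an unscheduled value at baseline is not itself a defect, since the last value before dosing serves a different purpose. The rule also applies alike to both arms of a double-blind study, and no direction of bias between arms is shown.

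**Conclusion.** The point holds as an internal conflict of limited reach. Followed literally, SAP 6.2.9 narrows the examination and ECG shift tables to the worst of at most three planned records, or the early-termination record. The tables can then understate abnormalities relative to their own description. This goes beyond a missing detail, because 6.2.9 is a stated rule with no exception for these tables.

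The size of the effect cannot be given. It depends on how many unscheduled ECGs and examinations were done, how many were worse than every scheduled record, and how many of those were not reported as adverse events; the documents give none of these. The overlap shares in the illustration describe how sparse the schedule is under assumed onset and duration, and should not be quoted as a loss rate. The importance is minor: a clarification worth making in a small proof-of-concept trial.

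**What to change.** **Correction.** Limit SAP 6.2.9 to by-visit summaries, and add one sentence saying that shift tables to the worst post-baseline record (6.15.4 and 6.15.5) use all post-baseline records: scheduled, repeat and unscheduled. Relabelling the tables as worst scheduled record would also remove the contradiction, but would leave the unscheduled findings out of the arm comparison.

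**Optional addition.** Add a worst-post-baseline laboratory summary by arm for the parameters named in Protocol 8.9: ALT, AST, total bilirubin and neutrophils. The planned laboratory shift tables classify values only as below, within or above normal, so a value beyond "Subjects will be discontinued from dosing if AST or ALT levels are >5 times the upper limit of normal" falls in the same category as a slight elevation.

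**Cost.** The correction takes one sentence, and the optional addition a few table rows. The data are already collected for the listings. Reported abnormality counts would rise slightly.

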#### 6.3 Conventions

All data listings, summaries, figures and statistical analyses will be generated using SAS version 9.4 or higher.

Summaries will be presented by treatment group. Treatment group labels will be displayed as follows:

- VERU-111 18 mg
- Placebo

Listings will be sorted in the following order treatment group, subject, parameter, and visit unless otherwise stated. All data will be listed, subjects who were not randomized will be displayed after the randomized treatment groups.

Continuous variables will be summarized by the number of non-missing observations, mean, median, standard deviation, and minimum and maximum.

Categorical variables will be summarized by presenting the frequency and percent. Percentages will be based on the number of non-missing observations or the subject population unless otherwise specified. For each variable, all categories will be shown. Zero frequencies (but not the percent) within a category will be presented.

QMD Ref: Worldwide-TMP-ST-005-7.0 Effective: 12Aug2019		Governing QMD: Worldwide-SOP-ST-001	
	Confidentiality Statement		
	This document is the property of Worldwide Clinical Trials Inc. and may not be duplicated, copied, altered or removed from company without		
	prior approval from Worldwide Quality Assurance or in compliance with Worldwide Standard Operating Procedures		

Worldwide Clinical Trials Controlled Quality Management Document		
WORLDWIDE CLINICAL TRIALS	Sponsor:	Veru Inc.
	Protocol Number:	V0211901
STATISTICAL ANALYSIS PLAN. PHASE 2-3-4		

#### **6.3.1** Decimal Places

Decimal places for derived data described in section 6.2 will be determined by the scale of measurement unless otherwise stated. No decimal places will be displayed if the smallest calculated value is  $\geq 100$ ; 1 decimal place will be displayed when the smallest value is within the interval (10, 100), with 10 being inclusive; 2 decimal places will be displayed when the smallest value is within (1, 10), with 1 being inclusive; and so on for even smaller scales of measurement.

Derived data where it is known in advance the result will be an integer for example day, month, year, number of days and total scores (for rating scales) will be presented with zero decimal places.

Means, medians and percentiles will be displayed to one more decimal place than the data, dispersion statistics (e.g. standard deviation) will have two more decimal places, and the minimum and maximum will be displayed to the same number of decimal places as reported in the raw data. Percentages will be displayed with one decimal place.

P-values will be quoted to 3 decimal places. P-values < 0.001 will be presented as p<0.001. Where this value is less than 0.05, 0.01 or 0.001, attention will be drawn to this fact using the conventional "\*\*", "\*\*" or "\*\*\*" annotation, respectively.

# 6.4 Subject Disposition

Subject disposition will be summarized as follows:

- The number of subjects, who entered the study, were randomized and who are in each analysis population will be summarized by treatment group and overall for the enrolled population.
- The number of subjects who failed screening and the reasons for failure will be tabulated for enrolled population.
- The number of early withdrawals and the reasons for withdrawals will be tabulated by treatment group and overall for the ITT population.
- The number of subjects present at each scheduled visit will be summarized by treatment group for the ITT population.

#### **6.5** Protocol Deviations

Protocol deviations will be summarized and listing of protocol deviations will be provided within Appendix 16.2 of the CSR.

QMD Ref: Worldwide-TMP-ST-005-7.0 Effective: 12Aug2019	Governing QMD: Worldwide-SOP-ST-001
Confidentiality Statement	
This document is the property of Worldwide Clinical Trials Inc. and may not be duplicated, copied, altered or removed from company without	
prior approval from Worldwide Quality Assurance or in compliance with Worldwide Standard Operating Procedures.	

Worldwide Clinical Trials Controlled Quality Management Document		
WORLDWIDE CLINICAL TRIALS	Sponsor:	Veru Inc.
	Protocol Number:	V0211901
STATISTICAL ANALYSIS PLAN. PHASE 2-3-4		

# 6.6 Baseline Comparability

The comparability of treatment groups with respect to subject demographics and baseline characteristics will be assessed in a descriptive manner, but no formal statistical testing will be performed.

Standard continuous or categorical variable summaries will be presented by randomized treatment group for the following variables based on the ITT population:

- Age (years) at Informed Consent
- Age category (<60 years, >=60 years)
- Sex (Female, Male)
- Fertility Status for Women (Childbearing Potential, Post-menopausal, Surgically Sterile)
- Ethnicity (Hispanic or Latino, Not Hispanic or Latino)
- Race (American Indian or Alaska Native, Asian, Black or African American, Native Hawaiian or Other Pacific Islander, White)
- Weight (kg) at Screening
- Height (cm) at Screening
- Body Mass Index (BMI) (kg/m^2) at Screening.

# 6.7 Medical History

Separate tabulations of previous and ongoing conditions will be presented by randomized treatment group and overall for the ITT population. Previous conditions are all conditions which ended before the first dose of study drug. Ongoing conditions are all conditions which were ongoing at the time of the first dose of study drug.

Conditions will be presented by Medical Dictionary of Regulated Activities (MedDRA, version 23.0 updated) primary system organ class and preferred term.

#### **6.8** Prior and Concomitant Medications

Separate tabulations will be produced for prior and concomitant medications presented by randomized treatment group and overall for the ITT population. Prior medications are defined as all medications ending before the date of first dose of study drug. Concomitant medications are defined as medications taken on or after the date of first dose of study drug.

QMD Ref: Worldwide-TMP-ST-005-7.0 Effective: 12Aug2019	Governing QMD: Worldwide-SOP-ST-001
Confidentiality	y Statement

Worldwide Clinical Trials Controlled Quality Management Document		
WORLDWIDE CLINICAL TRIALS	Sponsor:	Veru Inc.
	Protocol Number:	V0211901
STATISTICAL ANALYSIS PLAN. PHASE 2-3-4		

Prior and Concomitant medication verbatim terms (as recorded on the CRFs) will be mapped to Anatomical Therapeutic Chemical (ATC) Level 2 and Drug Reference Names using the WHO dictionary (version B3 Mar 2020).

Concomitant medications will be summarized using ATC Level 2 and preferred term.

### 6.9 Exposure to Study Drug

Extent of exposure (number of days of exposure to study drug) will be presented by randomized treatment group for the ITT population.

# **6.10 Treatment Compliance**

All subjects will receive standard of care plus oral daily VERU-111 or Placebo. Subjects will take one capsules per day.

Overall study drug compliance (%) will be summarized using descriptive statistics by treatment group and overall. Additionally, compliance (%) will be summarized as frequencies in '<80%' and '>=80%' categories.

Overall study drug compliance will be calculated as follows:

$$100*\frac{number\ of\ capsules\ taken}{planned\ total\ number\ of\ capsules}$$

where planned number of capsules is 1 capsules/day in both VERU-111 and placebo groups. Planned number of capsules will be calculated as last dose date – randomization date +1.

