8.10 Early Discontinuation of Study Treatment

A subject will be considered to have completed the efficacy portion of the trial if they received at least 21 days of treatment with study drug or the subject has been discharged from the hospital, or the subject has expired or the study is terminated by the sponsor. Subjects may prematurely discontinue study treatment for any of the following reasons:

- 1. Consent Withdrawn (specify the reason).
- 2. Significant and unacceptable adverse event specify the adverse event leading to discontinuation
- 3. Investigator decision (specify the reason), must be approved by the Medical Monitor
- 4. Non-compliance by subject with protocol requirements, must be approved by the Medical Monitor
- 5. Lost to follow-up (record the date of last contact)
- 6. Death (specify the following information)
 - a. Date of death
 - b. Death due to primary disease? Yes or no
 - c. Death due to study drug? Yes or no
 - d. Death due to adverse event? Yes or no
- 7. Study terminated by the Sponsor
- 8. Other reason (specify the reason) should be approved by the Medical Monitor

The reason for discontinuation of study treatment will be documented for each subject. Subjects who discontinue prematurely will not be replaced. If a subject is discontinued from the study, he will be asked to complete all End of Study visit assessments and return all study materials (study medication and electronic device). At the time of discontinuation, please fill out the End of Study case report forms (eCRFs) and subject disposition eCRF pages.

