12.2 Appendix B: Schedule of Study Evaluations

Day	Screen ^a	Day 1	Days 2-21	Days 3, 9, & 15	Day 16	Days 22 ^d and 29	Days 45 and 60
Informed Consent and	Х						
HIPAA							
Medical History	Х	Х					
Assessment of Eligibility	Х	Х					
Physical Exam	Х	Х		Xf		Х	
Vital signs	Х	Х	Х			Х	
Pregnancy test (female	Х		Xf			X ^g	
subjects only)				0			
12-lead ECG (single)	Х			X ^t		X	
Chest X-ray or CT		Х				Х	
Clinical Laboratory Tests							
Hematology	Х	Х		Х		Х	
Urinalysis	Х	Х				Х	
Serum Chemistry	Х	Х		Х		Х	
Temperature/SpO ₂	Х	Х	Xe			Х	
Dosing ^{b,c}		Х	Х				
Pharmacokinetic assessment				X ^{h, f}	X ^h		
Assessment of primary and secondary efficacy endpoints				\mathbf{X}^{f}		Х	Х
Assessment of conmeds	Х	Х	Х			Х	
Assessment of AEs		Х	Х			Х	X

a Screening evaluations are to be conducted within 2 days prior to Day 1.

b Subjects will be treated for 21 days OR until discharged from hospital

c Subjects can be discontinued if they are not responding to therapy d Early termination assessments the same as Day 22 assessments

e Temperature and SpO₂ will be taken every 12 hours on these days

f Day 15 only g Day 29 only

h Plasma samples for pharmacokinetic assessment will be taken at baseline (prior to dosing on Day 15) and at 4 hours (±2 hours), 12 hours (±2 hours) after dosing on Day 15, and at 24 hours (±2 hours) after dosing on Day 15 (prior to dosing on Day 16).

PROTOCOL SIGNATURE PAGE

Protocol Number:	V0211901
Protocol Date:	FINAL Amendment 6 (Version 7)/ 25 September 2020
Protocol Title:	Randomized, Placebo-Controlled, Phase 2 Study of VERU-111 for the Treatment of Severe Acute Respiratory Syndrome Coronavirus 2 (SARS-CoV-2) in Patients at High Risk for Acute Respiratory Distress Syndrome (ARDS).

SIGNATURE:

Sponsor

Date

Name and Title of Sponsor Representative

This signature of the Sponsor Representative constitutes approval of this protocol.

PRINCIPAL INVESTIGATOR SIGNATURE PAGE

Protocol Number:	V0211901
Protocol Title:	Randomized, Placebo-Controlled, Phase 2 Study of VERU-111 for the Treatment of Severe Acute Respiratory Syndrome Coronavirus 2 (SARS-CoV-2) in Patients at High Risk for Acute Respiratory Distress Syndrome (ARDS).
Protocol Date:	FINAL Amendment 6 (Version 7)/ 25 September 2020

SIGNATURE:

Principal Investigator:

Date

Name of Principal Investigator (Please Print)

Address of Principal Investigator

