#### 1 INTRODUCTION

This document details the planned statistical analyses for Veru Inc., protocol "V0211901" study titled "Randomized, Placebo-Controlled, Phase 2 Study of VERU-111 for the Treatment of Severe Acute Respiratory Syndrome Coronavirus 2 (SARS-CoV-2) in Patients at High Risk for Acute Respiratory Distress Syndrome (ARDS)".

The proposed analyses are based on the contents of the final version of the protocol (version 7.0, dated 25-SEP-2020). IND number: 149282.

This study is a multicenter, randomized, double-blind, placebo-control, efficacy and safety study of VERU-111 for the treatment of COVID-19.

This study consists of two treatment arms: VERU-111 18 mg treated group, and Placebo treated Group. Subjects will be randomized in a 1:1 fashion.

Subjects in the VERU-111 treatment group will receive standard of care, plus oral daily VERU-111 18 mg for 21 days or until released from hospital.

Subjects in the Placebo treatment group will receive standard of care, plus a placebo capsule for 21 days or until released from hospital.

VERU-111 18 mg dose will be supplied as capsules containing 18 mg of VERU-111. Capsules will be supplied in bottles containing 21 capsules in each bottle. Subjects will take one VERU-111 capsule per day.

Placebo capsules containing zero (0) mg VERU-111 drug substance will be supplied in bottles containing 21 capsules each. The placebo capsules will contain only anhydrous lactose, USP. These capsules are identically appearing to the VERU-111 capsules. Subjects will take one Placebo capsule per day.

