# **6.2.7** Exposure to Study Drug

Exposure to study drug will be calculated as the date of last dosing minus the first day of dosing + 1. The exposure calculation will not take into account breaks in therapy.

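### The planned-capsule count in SAP 6.10 runs from randomisation to the subject's own last dose, so it measures neither adherence to the planned course nor adherence while on treatment

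*SAP*

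**What the plan says.** SAP 6.10 defines overall compliance as 100 times capsules taken over the planned total. The rate is fixed: "where planned number of capsules is 1 capsules/day in both VERU-111 and placebo groups". The window is then fixed: "Planned number of capsules will be calculated as last dose date", minus the randomisation date, plus 1. Results are given as descriptive statistics and, in addition, "compliance (%) will be summarized as frequencies in '<80%' and '>=80%' categories". The output is Table 14.1.5.2 (SAP 11).

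The planned course is stated in both documents. SAP 1 has each arm treated "for 21 days or until released from hospital", and Protocol Appendix B notes "Subjects will be treated for 21 days OR until discharged from hospital". Stopping sooner for other reasons is foreseen in Protocol 8.10: "Subjects may prematurely discontinue study treatment for any of the following reasons". The list that follows includes adverse event, withdrawn consent, investigator decision and non-compliance.

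Elsewhere the SAP starts its clock at first dose. Study day does so in 6.2.2, and so does exposure in 6.2.7: "Exposure to study drug will be calculated as the date of last dosing minus the first day of dosing + 1".

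**The concern.** Both ends of the window are doubtful for something called planned. The last dose a subject took is an outcome. If it closes the denominator, doses never given after an early stop are never counted as planned, and only gaps before the stop (or a delay at the start) can lower the score. At the other end, days between randomisation and first dose count as capsules owed, although no study drug had been started.

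The two faults push in opposite directions. A subject who gave up treatment can sit above the 80% line, and one who took every dose can sit below it. At stake is whether the compliance table describes how much of the intended treatment was delivered. That is useful context in a proof-of-concept trial of about 40 subjects.

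**Working it through.** The documents give no compliance figure to reproduce, so the formula is evaluated directly.

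**Inputs**
- k = capsules taken, one a day (SAP 6.10).
- m = days missed between first and last dose; set to 0 below.
- L = days from randomisation to first dose. This is not given in the documents. Assumption: 0, 1 or 2 days. Protocol 8.2 (enrolment and randomisation) and 8.3 (Day 1, first dose) are separate steps with no same-day rule, and Protocol 7.3 ties dosing to the morning meal.
- Planned course: 21 days or until hospital release.

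**SAP formula.** The days from randomisation to last dose, inclusive, number k + m + L, so compliance = 100 × k / (k + m + L).

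**Early stop.** With m = 0 and L = 0 this is 100 × k / k = 100% for every k. The comparison depends on when the subject leaves hospital:

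| Doses before stopping | SAP, L = 0 | SAP, L = 1 | Planned course, in hospital to Day 21 |
|---|---|---|---|
| 5 | 5/5 = 100% | 5/6 = 83.3% | 5/21 = 23.8% |
| 10 | 10/10 = 100% | 10/11 = 90.9% | 10/21 = 47.6% |
| 15 | 15/15 = 100% | 15/16 = 93.8% | 15/21 = 71.4% |

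The last column is the extreme case. A subject who stops after 10 doses and is discharged on Day 12, with a dose due that day, has 10/12 = 83.3%. For a subject in hospital to Day 21, the 80% line is reached at 17 doses (17/21 = 81.0%; 16/21 = 76.2%). An uninterrupted stop at 16 doses or fewer would therefore change category.

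**Delayed first dose, nothing missed.** Compliance is 100 × k / (k + L), which is below 80% exactly when k < 4L.
- L = 1: k = 1, 2, 3 gives 50.0%, 66.7%, 75.0%. k = 4 gives 4/5 = 80.0%, which counts as at least 80%. k = 21 gives 21/22 = 95.5%.
- L = 2: below 80% up to k = 7 (7/9 = 77.8%). k = 8 gives 8/10 = 80.0%, and k = 21 gives 21/23 = 91.3%.

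Courses this short can be complete, because treatment ends at discharge.

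**With the window corrected** (first dose to the earliest of Day 21, discharge and death): the subject who stops after 10 doses and stays in hospital to Day 21 moves from 100% to 47.6%. The subject first dosed the day after randomisation and discharged after three consecutive doses moves from 3/4 = 75% to 3/3 = 100%.

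**The case against.** The best defence is that closing the window at last dose is a choice of measure. It describes adherence while on treatment and leaves duration to the exposure table. There is sense in this. Protocol 8.9 requires dosing to stop for specified liver-test, diarrhoea and neutropenia findings, and scoring such a subject against 21 days would present tolerability as non-compliance. For subjects dosed until discharge, last dose already marks the end of the planned course. But the defence does not save the formula as written. An on-treatment window would start at first dose, and SAP 6.10 labels its measure overall compliance against planned capsules.

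A reader might also infer more than the documents support:
- **That the 80% split decides who is analysed or how efficacy is judged.** Nothing says so. The mITT population requires at least 7 doses (SAP 6.1.4), the EE population rests on a signed evaluability form about study procedures (SAP 6.1.5), and no efficacy analysis refers to the percentage.
- **That early stopping would go unseen.** Exposure in days is tabulated by arm (SAP 6.9), early withdrawals are tabulated with reasons (SAP 6.4), and dosing and study completion are listed (SAP 11). What remains uncovered is narrower: exposure does not separate discharge on Day 10 from stopping on Day 10 in hospital, and SAP 6.4 counts withdrawals, not treatment stops.
- **That 24%, 48% and 71% are the usual error.** They require hospital stay to Day 21.
- **That any next-day first dose puts an adherent subject below 80%.** With a one-day lag this needs 3 or fewer doses. The lag itself is hypothetical: the screening window is counted back from randomisation in the Protocol Summary and from Day 1 in Appendix B, which suggests that the two nominally coincide.
- **That both effects apply in full together.** The 100% for stoppers needs no lag and the 75% needs a one-day lag; in very early stoppers they partly offset.

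**Conclusion.** The point holds, with limited reach. The denominator in SAP 6.10 fits neither the planned course nor an on-treatment window, and applied exactly it can place subjects on the wrong side of the 80% split.

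For uninterrupted early stoppers with a same-day first dose, the score is 100% whatever the stopping day. The overstatement against the planned course depends on discharge: for 10 doses it runs from about 17 percentage points (discharge on Day 12) to about 52 (hospital stay to Day 21). For adherent subjects with a delayed start, the understatement at 21 doses is 4.5 points with a one-day lag. It crosses the 80% line only at 3 or fewer doses, or 7 or fewer with a two-day lag.

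The consequence is confined to descriptive Table 14.1.5.2. No population, test or decision is stated to depend on it. The number of subjects affected cannot be worked out from the documents, which give neither the lag nor the frequency of in-hospital stops.

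**What to change.** Redefine planned capsules in SAP 6.10 as the days from first dose to the earliest of Day 21, hospital discharge and death, counting a discharge or death day only if a dose was due. Beside the percentage, report permanent treatment stops before that point with reasons, and show protocol-required stops separately so that tolerability is not read as non-compliance.

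If the sponsor prefers on-treatment adherence, keep last dose as the end, move the start to first dose, label the measure accordingly, and show the proportion of the planned course delivered next to it.

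The cost is one derivation line and a short addition to the table. Discharge and death dates are already needed for the hospital-stay and mortality endpoints, and Protocol 8.10 has the reason for stopping treatment recorded for each subject. Under the planned-course definition, reported compliance falls for subjects who stop early in hospital and rises for adherent subjects with a lag: slightly over a long course, more over a very short one.
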